This material is the property of the NYU School of Medicine and Langone Medical Center. Do not disclose or use except as authorized in writing by the study sponsor
Interventional Template Version: 11 January 2019

PANAS	Positive and Negative Affect Schedule
PDDS	Patient Determined Disability Scale
PI	Principal Investigator
QA	Quality Assurance
QC	Quality Control
RAVLT	Rey Auditory Visual Learning Test
RRMS	Relapse Remitting Multiple Sclerosis
SAE	Serious Adverse Event/Serious Adverse Experience
SDMT	Symbol Digit Modalities Test
SOP	Standard Operating Procedure
STAI	State-Trait Anxiety Inventory
tDCS	Transcranial Direct Current Stimulation
TLFB	Timeline Followback Method Assessment
US	United States
TMS	Transcranial magnetic stimulation

CONFIDENTIAL

This material is the property of the NYU School of Medicine and Langone Medical Center. Do not disclose or use except as authorized in writing by the study sponsor
Interventional Template Version: 11 January 2019

Protocol Summary

Title	A Telehealth tDCS Approach to Decrease Cannabis Use: Towards Reducing Multiple Sclerosis Disability
Short Title	A Telehealth tDCS Approach to Decrease Cannabis Use in MS
Brief Summary	We will recruit 52 patients with MS, CUD, and elevated distress (K10 score 10-35) in a double-blinded, parallel-arm, sham-controlled trial of a completely at-home intervention. We will test 20x20-minute RS-tDCS (2.0 mA, DLPFC: left anodal) paired with guided mindfulness meditation to decrease distress and cannabis use. Participants will be randomized 2:1 to active vs. sham tDCS.
Phase	Phase 2
Objectives	
- Evaluate the effect of DLPFC tDCS to decrease distress component of cannabis use disorder- Evaluate the effect of DLPFC tDCS to reduce cannabis use- Evaluate if DLPFC tDCS related change in cannabis use is linked to a change in distress
Methodology	2:1 Randomized, Parallel-Arm, Double-Blind, Sham-Controlled Design
Endpoint	
Primary Endpoints:
 
- Decrease in Distress by treatment End- Decrease in Cannabis Use by treatment End 
Secondary Endpoints:
 
-Decrease in Distress through 3-month follow-up-Decrease in Cannabis Use through 3-month follow-up
Study Duration	2 years
Participant Duration	Approximately 4.5 months (4-6 weeks of intervention + follow-ups at 1, 2, and 3 months)
Duration of IP administration	20x20 minutes daily sessions of DLPFC tDCS combined with mindfulness meditation
Population	N=52 female participants (ages 21-65) with RRMS and CUD
Study Sites	NYU Langone Health [name]
Number of participants	N=52 participants expected to be enrolled at NYU Langone Health
Description of Study Procedure	
tDCS is noninvasive brain stimulation device that modulate brain activity delivering a low-intensity electrical current (2.0 mA) through scalp sponge electrodes. Participants will follow an audio track for guided mindfulness during the stimulation.
 
For Active tDCS, the device is programmed to ramp up to 2.0 mA (for 30 seconds), provide constant current throughout session (19 minutes), and then ramp down (for 30 seconds) at the end.
 
For Sham tDCS the device is programmed to ramp up to 2.0 mA (for 30 seconds) followed by a ramp down (30 seconds), with no current delivery for 18 minutes, and then ramp up (for 30 seconds) and down (for 30 seconds) at the end.

Reference Therapy	

CONFIDENTIAL

This material is the property of the NYU School of Medicine and Langone Medical Center. Do not disclose or use except as authorized in writing by the study sponsor

[figure not shown]
Interventional Template Version: 11 JAN 2019

Key Procedures	Active or sham tDCS with simultaneous mindfulness meditation
Statistical Analysis	Multivariate linear regression will be used to evaluate the outcome of each Aim. The dependent measures will be nested within timepoint (Visit 1, 5, 10, 15, 20), with active/sham as fixed effects.

CONFIDENTIAL

This material is the property of the NYU School of Medicine and Langone Medical Center. Do not disclose or use except as authorized in writing by the study sponsor
Interventional Template Version: 11 January 2019

SCHEMATIC OF STUDY DESIGN

CONFIDENTIAL

This material is the property of the NYU School of Medicine and Langone Medical Center. Do not disclose or use except as authorized in writing by the study sponsor
Interventional Template Version: 11 January 2019

1 Key Roles

[name], Principal Investigator
NYU Langone Health — Neurology
[name]
[contact]
[contact]

[name]
NYU Langone Health — Neurology
[name]
[contact]
[name]

[name]
Wake Forest School of Medicine
[name]
[contact]
[contact]

2 Introduction, Background Information and Scientific Rationale

2.1 Background Information and Relevant Literature

Multiple sclerosis (MS) is a common neurological disorder, affecting over one million in the U.S. alone¹, many of whom are younger adults in the peak of their most productive years.

MS is a chronic and progressive CNS disease that is characterized by demyelination, immune-mediated inflammation, and neurodegeneration^{2,3}, and is without cure. It typically (85%) presents as relapsing-remitting, defined by acute episodes (e.g., motor and/or sensory dysfunction), followed by relative recovery and stability⁴. MS results in cumulative damage over time, with a broad and varying range of persisting symptoms^{5,6}. The aggregate daily impact of MS symptoms and reduced quality of life defines its disease burden⁷, which can result in devastating disability in otherwise healthy adults⁸⁻¹⁰. While MS disease-modifying therapies (DMTs) are valuable in slowing disease activity^{11,12}, they do not directly target its symptoms¹³.

Cannabis Use Disorder (CUD) is a common problem for people living with MS.

Cannabis use (smoking/vaping/ingestion) has grown exponentially in the U.S.¹⁴, further accelerated in the context of the COVID-19 pandemic¹⁵⁻¹⁷. While less likely than the general population to use alcohol or tobacco, more than one half of all patients with MS use cannabis¹⁸. The large majority of this use is outside of medical direction¹⁸, typically either as recreational or self-directed management of nonspecific problems (e.g., mood, pain, sleep). While cannabis is thought to be benign or even health-promoting among some patients with MS, it is only prescribed in a minority (~4%)^{18,19} where available^{20,21}, with insufficient evidence to support any therapeutic use in MS other than for spasticity^{22,23} (modest evidence for treating spasticity²⁴, insufficient for all other symptoms²⁵, including neuropathic pain²⁶). As a result, many patients with MS have become frequent and habitual users²⁷ in the cycle of addiction²⁸.

Cannabis use worsens MS disease burden²⁹.

While cannabis can vary widely in its ratio of its key components tetrahydrocannabinol (THC) and cannabidiol (CBD), both can dampen brain activity^{30,31} adversely influencing cognitive functioning^{32,33} and mood^{34,35}, and their respective neurobiological substrates^{36,37}. The problematic neuropsychiatric consequences are well known³⁷ and can be especially critical in the context of MS^{29,38-42}. The high prevalence of cannabis use in MS is a challenge for prospective study, with investigators instead demonstrating the therapeutic gains following its discontinuation, including restoration of aspects of brain activity⁴³, reduced depression⁴⁴, and improved cognitive functioning⁴³. The benefit to MS-related cognitive impairment is particularly urgent, given that it is among the most disabling disease features⁴⁵ and occurs in

CONFIDENTIAL

>75% of all patients at any point in their disease course^{46,47}. Initially characterized by slowed information processing⁴⁶, reduced cognitive functioning can be subtle but often disables otherwise neurologically intact patients, compromising the ability to meet both work and family responsibilities⁴⁸. Cannabis use causes further impairment^{37,49}, a finding that is consistent across other chronic brain disorders^{50,51}.

We propose to target the distress that perpetuates the addiction cycle.

Psychological distress⁵² is an emotional health status marked by negative affect (e.g., feeling anxious, agitated, tense, irritable). As described in Koob & Volkow's 3-stage model of addiction^{53,54}, negative emotional states^{52,55} are key drivers of the addiction cycle. Distress is a result of disordered cannabis use, and in turn, also drives its continued use (i.e. "to cope"). Distress resulting from the disordered use of cannabis is well documented^{56,57}, and patients with MS are likely to be at even greater vulnerability to the distress component of addiction⁵⁸⁻⁶². As the state of distress is often below the threshold of clinical depression or anxiety disorders, it remains an under-detected and undertreated aspect of the cannabis addiction cycle.

The dorsolateral prefrontal cortex (DLPFC) is a key neural circuit for negative affect⁶³⁻⁶⁶.

With growing knowledge of the neural circuits that contribute to treatment of substance use disorder in general^{63,67-69}, there is an emerging interest in neural circuits as a target for intervention⁷⁰. By targeting distress, we expect reduction in use of cannabis and corresponding improvements in subjective well-being⁷¹.

Investigations are currently focused on evaluating the efficacy of a variety of noninvasive brain stimulation techniques for application in substance use disorders, using transcranial direct current stimulation (tDCS)⁷² or transcranial magnetic stimulation⁷³ (TMS) as tools to modulate the DLPFC neural circuitry^{69,70}. We propose here the use of tDCS, where direct electrical current is delivered to cortical tissue via scalp electrodes with the goal of raising the resting membrane potential of the neurons and resulting in the higher likelihood of firing⁷⁴. In this manner, repeated applications of tDCS are used to modulate neuronal activity in regions of interest⁷⁵.

DLPFC tDCS has a strong body of evidence supporting its use for distress reduction.

Multiple RCTs have shown that repeated application (i.e., ≥ 20 daily sessions) of tDCS, targeting the DLPFC, reduces distress in other clinical disorders, such as in the context of depression⁷⁶ and anxiety⁷⁷ (and has received regulatory approval for clinical use in mood disorders in the EU, UK, Australia and Brazil⁷⁸). Further, we are currently leading the U.S. FDA-commissioned study of tDCS for depression using the Remotely Supervised tDCS (RS-tDCS) platform as proposed here^{79,80}. Our extensive experience with tDCS in patients with MS, and without depression, has shown that the DLPFC tDCS (vs. other targets such as primary motor cortex) reliably decreases negative affect. Importantly, these changes have also been linked to increased functional connectivity in the DLPFC following treatment⁸¹.

tDCS must be dosed in a sustained and cumulative manner for adequate evaluation of its efficacy.

It is clear that tDCS effects are cumulative with adequate evaluation of behavioral effects requiring a period of multiple repeated applications⁸². Preclinical studies have demonstrated that stimulation results in sustained neuronal response⁷⁵, with increased sensitization following repeated application⁸². This effect is mirrored through consistent findings across clinical studies in that: **1)** a single tDCS session doesn't cause any meaningful behavioral response, and **2)** behavioral changes only follow a sustained period of daily treatment^{83,84}.

[figure not shown]
2.2 Name and Description of the Investigational Device

- **1x1 Mini-CT tDCS device (Soterix Medical Inc.):** The 1x1 Mini-CT tDCS device (see Fig.1, *Panel A*), through the accompanying headset (Fig. 1, *Panel B*) and sponge electrodes (Fig.1, *Panel C*), delivers a weak electrical current (1.0-2.0 mA) to target a specific area of the brain. It is a powered device (9 V) and is easily operated, with a user-friendly large-button keypad interface. The device has specific functions and features that guarantee safety in the remote supervised administration and uniform stimulation dose across sessions and participants. The device allows strict dose

CONFIDENTIAL

control and usage control, employing a one-time use code provided by the study technician to unlock the device for each stimulation session.

Figure 1. Equipment for tDCS intervention

2.2.1 Preclinical Data

[figure not shown]
N/A

2.2.2 Clinical Data to Date

Feasibility of RS-tDCS. We have led the field in home-based brain stimulation with the development of the RS-tDCS platform⁸⁵⁻⁹⁵. In our protocol, participants are provided with remotely-controlled tDCS device, trained in safe and effective operation, and then supervised for daily use through live videoconference⁹⁶

(VSee⁹⁶). Our updated videoconference will be Zoom or Webex. The telehealth connection has resulted in high retention rates across repeated and extended sessions (e.g., >97% completion rates across RCTs to date⁸⁵⁻⁹⁵). Extensively tested over > 7 years (>9000 at-home tDCS sessions in >400 patients to date), it is well validated for use in MS and generalizable for use across most other clinical populations⁸⁵⁻⁹⁵ (ages 18-80 years, range of neurological and psychiatric conditions, including those with advanced disabilities and/or limited technical experience, and reaching those at socioeconomic disadvantage). Further, the RS-tDCS platform has allowed for continued enrollment of patients with MS in ongoing RCTs during the COVID-19 onsite clinical research pause⁹⁷⁻¹⁰⁰ (with >100 participants by completing all study procedures from home).

Figure 2. 20 RS-tDCS DLPFC sessions significantly reduces negative affect in an MS sample

DLPFC tDCS regulates negative affect. DLPFC tDCS has been established to reduce distress (e.g., in mood disorders^{101,102} and other psychiatric conditions¹⁰³). In subanalyses of nondepressed MS participants with high baseline negative affect⁵⁵, 10 or more RS-tDCS sessions, led to reliable negative affect reduction (Fig. 2), and the negative affect reduction was maintained at 1-month follow-up. Importantly, these changes have also been linked to increased functional connectivity in the DLPFC following treatment⁸¹.

2.2.3 Dose Rationale

The tDCS protocol of this proposed research will use a stimulation intensity of 2.0 mA that falls well within safety limits established by numerous previous studies applying tDCS with human subjects.

CONFIDENTIAL

This material is the property of the NYU School of Medicine and Langone Medical Center. Do not disclose or use except as authorized in writing by the study sponsor
Interventional Template Version: 11 January 2019

2.3 Rationale

The application of tDCS to substance use disorder is not novel on its own⁷⁰. However, no study to date has evaluated tDCS for the treatment of CUD¹⁰⁴, and all studies of tDCS in other substance use disorders have required onsite delivery of treatment, resulting in mixed findings following “underdosed” treatment periods in terms of number of applications (i.e., <5) and duration of treatment period (i.e., 1 week or less)¹⁰⁵. Further limiting comparison/conclusion across studies to date has been the broad variation in other parameters such as electrode montage, stimulation intensity, duration, frequency, and concurrent activity during the stimulation^{70,104}. tDCS represents a promising treatment to reduce the distress component of the addiction cycle, and must be evaluated in a dosage that is likely to be effective.

Hypothesis: When given in a multisession paradigm, active vs. sham tDCS delivered to the DLPFC will reduce distress and cannabis use in patients with MS.

[figure not shown]
2.4 Potential Risks & Benefits

2.4.1 Known Potential Risks

- Risks of tDCS:** The repeated application of tDCS as proposed in this study poses a non-significant risk (NSR) to participants. The safety of this technique has been addressed and tested by multiple researchers who have concluded that tDCS, as applied in a manner similar to our proposed protocol, induces only mild and transient side effects with no report of serious adverse event related to tDCS across clinical trials to date. In >9,000 participant, no undesirable or long-lasting effects have been reported, nor have any subjects reportedly abandoned a study due to discomfort. The most common side effects are warming sensation, itching or tingling sensation under the area of the electrodes. The tDCS protocol of this proposed research will use a stimulation intensity of 2.0 mA that falls well within safety limits established by numerous previous studies applying tDCS with human subjects. In both active and sham tDCS treatment arms, there could be mild discomfort from wearing the headgear.

The protocol is designed to have a decision-tree series of checkpoints with "STOP" criteria that must be cleared in order to proceed at each step (see Fig.3).

Figure 3. Safety and Tolerability checkpoints and stop criteria

CONFIDENTIAL

This material is the property of the NYU School of Medicine and Langone Medical Center. Do not disclose or use except as authorized in writing by the study sponsor
Interventional Template Version: 11 January 2019

- **Guided mindfulness meditation:** Mindfulness meditation is not associated with any known risk. To minimize possible frustrating feeling, each session will be monitored in real-time via HIPAA-compliant videoconference with a trained study technician.
- **Self-report questionnaires:** Completing questionnaires about one's physical and mental health and cannabis use may produce some discomfort and/or emotional distress in some patients. Participants will be allowed to take breaks as needed and may skip questions they do not feel comfortable answering so long as the questions do not affect analysis of primary endpoints or eligibility criteria. While we don't anticipate this population to have suicidal ideation, [name] MD will screen for suicidality as part of the research eligibility screening and will follow standard clinical procedures if a subject is suicidal (e.g. refer subject to closest emergency room).
- **Single panel urine test:** Completing the procedure for urine strip testing in the context of video visit may cause some emotional discomfort. Participants may become upset if the results of the strip test are not consistent with their self-reported use.

2.4.1.1 Other Risks

- **Breach of Confidentiality:** There is minimal risk of breach of confidentiality. Participants will be assigned a unique study ID and their name will not be used on any of the data collected. All study data survey will be acquired through REDCap and the printed records will be stored in lock cabinet at [name]. Any study data stored on secure NYU computers and servers will be de-identified. The results of these data collected may be used for publication but will not include the participants' names. Drug test results will not be added to subjects' medical records and will not be stored with any PHI.
- **Unforeseeable Risks:** While not expected, there may be risks associated with tDCS that are not known at this time.

2.4.2 Known Potential Benefits

Some participants may receive benefit from the mindfulness meditation program. There is robust research on the mental health benefits of mindfulness meditation (e.g. reduced distress and anxiety).

Other potential benefits include a telehealth screening with a licensed clinician that could be of benefit to subjects if the results of these evaluations are utilized in their future health care.

This will be the first study to evaluate a tele-intervention program of tDCS for reducing distress and cannabis use in MS. The project has the potential to produce an immediately available treatment option for distress and CUD that could be generalized to other substance use disorders. This would have immediate and significant clinical utility. In particular, the benefit to the field is the availability of treatment option for managing symptom burden, generalizable to the common use of cannabis in other chronic brain conditions, and generalizable across those who have substance use disorder.

3 Objectives and Purpose

3.1 Primary Objective

- To evaluate the effect of active DLPFC RS-tDCS to decrease the distress component of CUD in MS.
- To evaluate the effect of DLPFC tDCS to reduce cannabis use in MS.

CONFIDENTIAL

This material is the property of the NYU School of Medicine and Langone Medical Center. Do not disclose or use except as authorized in writing by the study sponsor
Interventional Template Version: 11 January 2019

3.2 Secondary Objectives

- To evaluate the presence of persisting benefits in distress through the 3-month follow-up.
- To evaluate the presence of persisting benefits in cannabis use through the 3-month follow-up.
- To evaluate the interactions between the dependent measures of the primary objectives. The interactions between the dependent measures will be evaluated to test the hypothesis that an RS-tDCS-related change in cannabis use metrics is linked to a change in distress.
- To evaluate the interactions between distress and cannabis use and the exploratory outcomes of cognitive and symptom measures.

4 Study Design and Endpoints

4.1 Description of Study Design

This randomized, double-blinded, parallel-arm, sham-controlled study will recruit n=52 female MS patients (target is 42 patients plus 10% to account for screen fails and withdrawals) to be randomly assigned using a 2:1 randomization method to receive 20x20 min sessions of either active 2.0mA tDCS or sham tDCS, combined with simultaneous mindfulness meditation over a 4-6 week period. Groups will be matched on years of cannabis use (4 years or less vs. 5 or more years).

All participants will have a remote consent/research screening visit, baseline visit, 20 tDCS treatment visits, and 1-month, 2-month, and 3-month follow-ups. All visits will be completed remotely through Zoom or Webex. Study procedures will be the same for both groups, with the only difference being the tDCS stimulation setting of 2.0 mA active or sham.

This will be a single site study at NYU Langone Health and will take place over a 2 year period.

4.2 Study Endpoints

4.2.1 Primary Study Endpoints

- Change in distress measured by Kessler Psychological Distress Scale (K10) and Positive and Negative Affect Schedule (PANAS) between baseline and treatment-end.
- Change in cannabis use measured by Timeline Followback Method Assessment (TLFB), Marijuana Craving Questionnaire (MCQ-17), Daily Sessions, Frequency, Age of Onset, and Quantity of Cannabis-Use Inventory (DFAQ-CU) and Cannabis Withdrawal Scale (CWS) between baseline and treatment-end.

4.2.2 Secondary Study Endpoints

- Change in distress measured by K10 and PANAS across the 3-month follow-up to assess sustained improvement.
- Change in cannabis use measured by TLFB, MCQ-17, DFAQ-CU and CWS across the 3-month follow-up to assess sustained improvement.
- Evaluate the relationship between change in cannabis use metrics and change in distress.

4.2.3 Exploratory Endpoints

- Interaction between change in depression and/or cannabis use and MS symptoms (SymptoMScreen) and cognitive measures (BICAMS, Cogstate Brief Battery).

CONFIDENTIAL

This material is the property of the NYU School of Medicine and Langone Medical Center. Do not disclose or use except as authorized in writing by the study sponsor
Interventional Template Version: 11 January 2019

5 Study Enrollment and Withdrawal

5.1 Inclusion Criteria

In order to be eligible to participate in this study, an individual must meet all of the following criteria:

1. Ages 21-65 (inclusive)
2. Female
3. Seeking treatment to reduce or discontinue current cannabis use (smoke/vape/ingest)
4. Current Cannabis Use Disorder per DSM-V
5. K10 score 10-35, inclusive (mild to high moderate distress)
6. Definite MS diagnosis, relapsing remitting (RRMS) subtype
7. PDDS score 0-7 (mild to moderate neurological disability, established to be able to complete procedures)
8. All medications stable for \geq 1 month prior to enrollment and throughout the trial
9. Ability to understand the informed consent process and provide consent to participate in the study
10. Stable and continuous access to internet service, email (WiFi “hotspot” to be provided if needed)
11. Ability to use mobile devices
12. Fluent in English language (due to outcomes validated in English versions only)
13. WRAT-4 score \geq 85

Inclusion criteria may be confirmed through medical records, screening assessments and self-report.

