8.2 Study Assessments

8.2.1 Distress/Mood Assessments

- Kessler Psychological Distress Scale (K10)¹²¹: 10-item questionnaire intended to yield a global measure of distress based on questions about anxiety and depressive symptoms that a person has experienced in the past 4 week period.
- Positive and Negative Affect (PANAS)¹²²: 20-item self-report questionnaire that measures positive and negative affect.
- Beck Depression Inventory (BDI)¹²³: it is a self-report instrument intended to assess the existence and severity of symptoms of depression.
- State-Trait Anxiety Inventory (STAI)¹²⁴: it is a psychological inventory based on a 4-point Likert scale and consists of 40 questions on a self-report basis to assess anxiety and trait anxiety.

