8.3 Study Schedule

8.3.1 Pre-Screening

- Team member conducts phone pre-screening (including WRAT-4, K10, and MS-PDSS) to determine general eligibility based on inclusion/exclusion criteria. Completing these measures over the phone is a practical option that helps screen out those who are ineligible before shipping study materials and it is suitable for phone use as participants can verbally respond to each scale.

On the K10, those who score in the severe mental disorder range (36-50) will be offered to contact the NYU Langone Psychiatry Associates at [contact], or if outside the NY area the Substance Abuse and Mental Health Services Administration (SAMHSA) hotline at [name].

All data collected for the purposes of the eligibility pre-screening will be destroyed immediately if the potential subject is ineligible or does not sign an informed consent form at their baseline.

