10.5 Sample Size

Power analyses were conducted independently for Aim 1 and Aim 2, wherein estimated effect sizes came from 2 independent manuscripts that used tDCS to measure changes in distress (Aim1) and estimated changes in cannabis use (Aim 2). In the planned study subjects will be assessed at 5 time points with the Change from V1 being used as a dependent variable (4 pieces of data per dependent measure per participant).

There is an anticipated interclass correlation coefficient (ICC) of 0.8 for the within-subjects measures. The design effect which accounts for multiple correlated observations within each subject, is estimated to be 4.2 ($DE = [1 + (5-1) 0.8]$). In a clustered setting, the sample size is $N_{\text{effective}} = nm/DE$ where n is the number of subjects required when m replications within participants are performed after accounting for the design effect (DE). The estimated number of individuals needed to detect an effect in the active RS-tDCS group is 28 for Aim 1 and 15 for Aim 2 (1-sided alpha of 0.05 and power of 80%).

CONFIDENTIAL

This material is the property of the NYU School of Medicine and Langone Medical Center. Do not disclose or use except as authorized in writing by the study sponsor
Interventional Template Version: 11 January 2019

For this study, we will utilize a 2:1 randomization based on pragmatic considerations including timeline, cost, and the added value of over recruiting to the Active group in order to have a better assessment of safety and tolerability data. In corporation this information into the total planned recruitment size, we arrived at n=42(=50 * 4.2 / 5). (28 allocated to active, 14 allocated to sham). We anticipate enrolling 52 participants which includes 10% drop out rate.

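### The K10 entry range of 10-35 probably starts at the scale minimum, so it caps distress without requiring it, and the Aim 1 model has no baseline K10 term

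*Combined protocol and SAP*

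**What the plan says.** Section 5.1, criterion 5, admits "K10 score 10-35, inclusive (mild to high moderate distress". The Protocol Summary describes the same people as having "elevated distress (K10 score 10-35". No other inclusion criterion sets a minimum on any distress or mood scale.

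Section 8.2.1 calls the K10 a "10-item questionnaire intended to yield a global measure of distress". Section 8.3.1 offers a referral contact to "those who score in the severe mental disorder range (36-50", which is the band just above the entry limit. Neither section gives the item scoring or the lowest possible total.

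The first primary endpoint in section 4.2.1 is "Change in distress measured by Kessler Psychological Distress Scale (K10) and Positive and Negative Affect Schedule (PANAS) between baseline and treatment-end". The second is cannabis use, measured on four instruments. Section 10.5 describes the analysis variable as "Change from V1 being used as a dependent variable". Section 10.4.2 fits a linear mixed model with treatment arm as the fixed effect and names no baseline term; its only covariate is elapsed days, for the interval effect sizes. Section 10.4.1 considers baseline characteristics as covariates only for supportive and secondary analyses. The supplementary list in section 10.2 includes BDI, STAI and CUDIT-R but not baseline K10.

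**The concern.** An entry range meant to select distressed patients should have a lower limit that excludes someone. If 10 is the lowest possible K10 total, this one excludes nobody, and the criterion acts only as a cap. Three things then follow.

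- The population label does not match the criterion. A result would be reported for patients with elevated distress although the entry rule did not require any.
- The supporting MS data in section 2.2.2 come from patients whose negative affect was high at baseline. The entry rule does not reproduce that selection, so that result may not carry over.
- Participants at or close to the minimum have little or no room to decrease on the K10. This would pull the K10 effect size towards zero, and section 10.4.2 says that providing effect sizes for the next grant is the purpose of the pilot.

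**Working it through.** **Where the scale starts.** The inputs are 10 items (8.2.1), a highest named total of 50 (8.3.1) and an entry range of 10-35 (5.1). The common item scorings give:

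| Item scoring | Total range | Fits a top band of 36-50? | Room to decrease from 10 |
|---|---|---|---|
| 0 to 4 | 0-40 | No | not applicable |
| 1 to 5 | 10-50 | Yes | 0 points |
| 0 to 5 | 0-50 | Yes | 10 points |

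The entry range has 35 − 10 + 1 = 26 values and the excluded band has 50 − 36 + 1 = 15. Together they make 41, which is every value from 10 to 50 (50 − 10 + 1 = 41). The two bands tile the 1-to-5 scale exactly, so a minimum of 10 is the most plausible reading. The documents do not rule out 0-to-5 scoring. Under that scoring the limit would exclude totals of 0 to 9, and a score of 10 would be one fifth of the range.

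**The plan's own sample size.** Section 10.5 gives a design effect of 1 + (5 − 1) × 0.8 = 4.2 and N = 50 × 4.2 / 5 = 42, split 28 and 14. This reproduces. No K10 effect size or SD is given, so the power behind it cannot be rebuilt.

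**Illustration of a floor.** Assume a simple comparison of 28 with 14 at one-sided 0.05 that has exactly 80% power when nobody is at the floor. Assume also that a share f enters at the minimum and shows no K10 change, with the SD unchanged.

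- √(1/28 + 1/14) = 0.327, so d = (1.645 + 0.842) × 0.327 = 0.814.
- Power = Φ((1 − f) × 0.814 / 0.327 − 1.645).
- N needed to keep 80% = 42 / (1 − f)², rounded up.

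| f | Power | N needed |
|---|---|---|
| 0% | 80.0% | 42 |
| 5% | 76.3% | 47 |
| 10% | 72.3% | 52 |
| 20% | 63.5% | 66 |
| 30% | 53.8% | 86 |

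Neither f nor d is in the documents.

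**What a baseline term would do.** With arms of 28 and 14, the standard error of the chance difference in mean baseline K10 is 0.327 SD, so a visible imbalance would be unremarkable. Let ρ be the correlation of baseline with a later score, with equal variances. The variance of a change score is 2(1 − ρ) and that of a baseline-adjusted score is 1 − ρ², so their ratio (adjusted to change) is (1 + ρ)/2. If the ICC of 0.8 in section 10.5 is read as ρ, the ratio is 0.90, a 10% smaller residual variance. At ρ = 0.5 (assumed) it is 0.75.

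**The case against.** Several stronger readings are tempting, and the documents do not support them.

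- **That these participants cannot improve on the primary outcome.** There are two primary endpoints with several measures. A woman at K10 = 10 can still improve on PANAS negative affect, TLFB, MCQ-17, DFAQ-CU and CWS.
- **That everyone near the floor contributes nothing.** Only a score of exactly 10 rules out a decrease; scores just above it limit it. The test in section 10.2 is a treatment-by-time interaction, so a participant at the floor can still contribute if sham patients worsen. Eligibility K10 is also taken by phone at pre-screening, and a 10 there need not be a 10 at V1.
- **That the trial loses a known amount of power.** The share at the floor is not given. Section 5.1 requires current cannabis use disorder and treatment-seeking, and section 2.1 argues that such patients carry distress, so the share may be small. It is also unknown whether the planning effect came from a sample free of floor scores.
- **That the limit should simply move to where the sponsor's mild band begins.** The only such banding in the documents is criterion 5 itself, which starts mild at 10. That change would alter nothing.

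It is also fair to say that the scale minimum is inferred, and that section 10.4.1 already allows baseline covariates in supportive analyses. What these objections leave standing is the mismatch between the label and the criterion, and the missing baseline term in the primary model.

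**Conclusion.** The point holds in a limited form. If K10 items are scored 1 to 5, as the named bands suggest, criterion 5 sets an upper limit on distress and no effective lower one, contrary to the summary's description of the population. If they are scored 0 to 5, the limit does some work and only the weaker question remains of whether one fifth of the range counts as elevated.

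The direct consequence is confined to the K10: a participant entering at the minimum cannot decrease on it. The power figures show how the loss would scale with the share at the floor and are not a forecast. The lack of baseline adjustment in the primary model does not depend on the scoring assumption. It is worth correcting in its own right with a sham arm of 14.

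**What to change.** 1. **Model.** In section 10.4.2, add V1 K10 as a covariate in the primary Aim 1 K10 model, and V1 negative affect in the PANAS negative affect model. Both are already collected, so the cost is one sentence and one extra fixed term per model. This gains precision and removes chance baseline imbalance. It does not give floor participants room to decrease, so it does not replace items 2 and 3.
2. **Scoring.** State the K10 item scoring and its lowest and highest totals in section 8.2.1. This costs one line.
3. **Label.** Reconcile criterion 5 with the Protocol Summary in one of two ways. The sponsor may set and justify a lower limit above the scale minimum; this needs an eligibility amendment and loses whatever share of otherwise eligible patients falls below it, which the documents do not let one estimate. Or the sponsor may keep the range and drop elevated distress from the population description, so that conclusions are not claimed for a distressed population that the criterion does not select. The second route costs only wording.
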